9.5 Definition of Screening

Screening during the 52-week treatment period for the PA: last non-missing value before baseline.

9.6 Definition of Baseline

- Baseline during the 52-week treatment period for the PA: last non-missing value on the day of or prior to first administration of evobrutinib or placebo. Of note, time of first dosing administration and assessment of baseline (both done on the same baseline day) will not be used in the determination of baseline value, unless otherwise specified for specific analysis.
- Baseline during the LTE period for the LTE analysis: the baseline of the 52-week treatment period will be used.

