9.2 Presentation of Tables/Listings/Figures (TLFs)

Tables and figures will be sorted by treatment group (in the order stated in Table 6) and chronological time point (where applicable).

Table 6: Treatment Groups and Regimens

Treatment Group	Regimen	Presentation for the PA	Presentation for the LTE analysis (*)
1	Placebo	Placebo	Placebo/Evobrutinib 50 mg BID
2	Evobrutinib 25 mg QD (once daily)	Evobrutinib 25 mg QD	Evobrutinib 25 mg QD/Evobrutinib 50 mg BID
3	Evobrutinib 75 mg QD	Evobrutinib 75 mg QD	Evobrutinib 75 mg QD/Evobrutinib 50 mg BID
4	Evobrutinib 50 mg BID (twice daily)	Evobrutinib 50 mg BID	Evobrutinib 50 mg BID/Evobrutinib 50 mg BID

(*): Subjects who complete the 52-week Double-blind placebo-controlled period will be offered participation in an optional open label, LTE period for an additional 2 years. During this LTE period, subjects will be administered evobrutinib at an initial dose of 50 mg BID or the eventual Phase III dose, when decided.

All data recorded during the trial will be presented in individual data listings (in the order stated in Table 6). All listings are sorted by treatment group, subject, and time point (where applicable), if not otherwise stated.

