9.7 Other Specifications

Derivation of Age (years):

Age will be derived according to the following formula:

$$\text{Age (Years)} = \frac{(\text{date of given informed consent} - \text{date of birth} + 1)}{365.25}$$

In case of missing day for the date of birth, but month and year available, the day of birth will be set to 1 in the formula above. In case of missing day and month, they will both be set to 1.

Definition of Change from Baseline (CFB):

CFB and percent CFB will be computed as follows:

- CFB = visit value – baseline value
- Percent CFB = 100 * (visit value – baseline value) / baseline value

Definition of duration:

Unless otherwise specified, duration will be calculated as the difference between start and stop date + 1 (eg, duration of AE (days) = AE stop date – AE start date + 1). Unless otherwise specified, missing dates will not be imputed.

Conversion factors:

The following conversion factors will be used to convert days into months or years: 1 month = 30.4375 days, 1 year = 365.25 days. For time windows calculation, 1 month is expressed as 30 days.

Definition of Body Mass Index (BMI) (kg/m²):

BMI is defined as weight / (height²), where weight is expressed in kg and height in m. The BMI is available in the vs1 form of the Case Report Form, electronic (eCRF) and will not be re-derived.

Handling of missing data:

For efficacy analysis, methods of missing data handling are detailed in Section 14.

Unless otherwise specified, missing data will not be replaced.

In all subject data listings, imputed values will be presented and will be flagged. Non-imputed partial dates will be presented in a format such as “____YYYY”. Where imputation is defined, an imputed date with flag (i.e., D for day, M for month) will be reported.

Missing statistics, e.g., when they cannot be calculated, should be presented as ‘nd’ (denoting “Not Done”). For example, if n=1, the measure of variability (SD) cannot be computed and should be presented as ‘nd’. In case of zero records, an empty output with 0 occurrences, or a sentence mentioning that there are no data, will be presented. For tables of AEs and Deaths (outputs required for EudraCT and/or clinicaltrial.gov), if there are no observations, the output must contain the first line ‘Subjects with...’ or ‘Subjects who died’ displayed with 0 occurrence.

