If the System Organ Class (SOC) or Anatomical Therapeutic Class (ATC) term is missing/not coded yet, then ‘Uncoded SOC’ (or ‘Uncoded ATC’) will be indicated at the TLF level. When a Preferred Term (PT) is missing, it will be set to ‘Uncoded PT: verbatim text’.

Treatment day:

Treatment day is defined as relative day to the start date of treatment. Treatment day will be calculated as the number of days since the first administration of any IMP. The day before is defined as Treatment day –1 (no Treatment day 0 is defined). Treatment day will only be presented in subject safety data listings.

For the 52-week treatment period, start date of treatment is defined as the date of first administration of randomized study drug.

For the LTE treatment period, start date of treatment is defined as the date of first treatment administration on or after the date of end of 52-week treatment.

On-Treatment flag:

On-treatment values are results of assessments done from the first IMP administration on Day 1 till End of Study (completion or early termination).

Repeated and unscheduled measurements:

Repeated and unscheduled measurements are included in the listings. Data collected at both unscheduled and scheduled visits will be used for shift tables. For summary statistics, figures, or inferential analysis, data are re-allocated to an analysis visit using time window calculations (see below).

Gap between 52-Week treatment period and LTE treatment period:

Subjects with a gap greater than or equal to 2 weeks between 52-Week treatment period and LTE period will be analyzed the same way as subjects without a gap. The gap will be defined using the last dose received during the 52-week treatment period and the first dose received during the LTE treatment period. Specific data listings on safety data (AEs and laboratory data) collected during the gap period will be produced for these subjects for the LTE analysis. In addition, for the subgroup of subjects with a gap greater than or equal to 2 weeks, the following analyses will be provided:

- Summary statistics of the gap duration
- SLE disease baseline characteristics at LTE Day 1
- SRI-4 response and SRI-6 response among HDA subjects by LTE visit

Time windows:

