Time to first flare, flare-free status and annualized flare rate	
Time to first flare, flare-free status and annualized flare rate will be analyzed as in Section 14.3.2 at Week 24, Week 52 and Week 104 with descriptive statistics only. No statistical modeling will be performed.
 
Time to first flare will be assessed starting from randomization (Day 1 of 52-week treatment period) and will be derived for the whole treatment period.
 
Flare analyses will be censored at the time of announcements to the sites of study early termination (i.e. 23 March 2020)

15 Safety Evaluation

For all safety endpoints, data selection for PA and LTE analysis will be handled as indicated in the [Table 26](#).

Table 26 : Data Handling for Safety Analysis

Data summarized	Analysis	Analysis sets	Period covered	Treatment groups

 • AEs • Laboratory data • Vital signs • ECGs • Other safety evaluations 	PA	SAF	All data from 52-week treatment period (safety follow-up included)	
 • Placebo • Evobrutinib 25 mg QD • Evobrutinib 75 mg QD • Evobrutinib 50 mg BID
	LTE analysis	LTE SAF	All data from LTE period (safety follow-up posterior to LTE included)	
 • Placebo/Evobrutinib 50 mg BID • Evobrutinib 25 mg QD/Evobrutinib 50 mg BID • Evobrutinib 75 mg QD/Evobrutinib 50 mg BID • Evobrutinib 50 mg BID/Evobrutinib 50 mg BID

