15.3 Clinical Laboratory Evaluation

The following laboratory parameters will be measured during the trial as part of the safety evaluation:

- Hematology,
- Biochemistry, including the following supplementary liver function tests (LFT):
 - Aspartate aminotransferase,
 - Alanine aminotransferase,
 - Alkaline phosphatase,
 - γ -Glutamyl-transferase,
 - Bilirubin (total),
- Urinalysis,
- Coagulation.

The clinical laboratory safety tests to be measured in this trial are provided in the protocol (refer to Section 7.4.3 Table 11 of the CTP). Parameters from the Section 7.4.3 of the CTP to be summarized and listed in the TLFs are provided in Appendix 18.12.

All laboratory data results will be presented using international system of units (SI).

Clinical laboratory findings (hematology, biochemistry, urinalysis, coagulation) will be summarized by treatment using descriptive statistics at baseline and each post baseline visit for absolute value and changes from baseline (see Section 8.2.3), excluding coagulation laboratory findings which will be summarized only at the screening visit.

Some laboratory results will be classified according to NCI-CTCAE Version 4.03 as provided by the central laboratory. In case a laboratory parameter has bi-directional toxicities (e.g., Potassium) both directions will be presented for the given parameter (i.e., Potassium Low and Potassium High).

On-treatment values are results of assessments done from the first IMP administration on Day 1 till End of Study (completion or early termination).

Laboratory results containing a modifier such as “<” or “>=” will be handled case by case for summary statistics (see Appendix 18.13) and will be reported as collected in the database and as imputed in subject data listings.

A shift table of baseline versus post-baseline based on the worst NCI-CTCAE grade will be presented by treatment group for hematology and biochemistry.

Subject data listings will be provided, with a flag for abnormal values, along with corresponding normal ranges:

- Laboratory gradable parameters part of NCI-CTCAE will be presented according to the categories based on normal ranges along with the grade. Abnormal values will be flagged according to the direction of toxicity as detailed in Appendix 18.12 (e.g., for a parameter such as Potassium Low, only values below the LLN will be flagged).

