15.8 Serum IgG, IgA, IgM Levels

Boxplots of Serum IgG, IgA and IgM levels (g/L) by treatment group and time point will be provided, as well as Line plots of median percent change from baseline by time point and treatment group.

Descriptive statistics (absolute value, change from baseline and percent change from baseline) by treatment group and time point will be performed as well.

Serum IgG, IgA, IgM and IgG subclass levels will be listed by treatment group, subject and time point (where applicable). IgG values < 3 g/L (severe hypogammaglobulinemia) and IgG values < 6 g/L (hypogammaglobulinemia) will be flagged in the listing.

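### LTE safety shift tables for subjects switched from placebo use a baseline about a year before their first evobrutinib dose, so they cannot separate the placebo period from the evobrutinib period

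*SAP*

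**What the plan says.** The LTE rule in SAP Section 9.6 is "Baseline during the LTE period for the LTE analysis: the baseline of the 52-week treatment period will be used". The same section defines that 52-week baseline as the "last non-missing value on the day of or prior to first administration of evobrutinib or placebo", so for a placebo subject it precedes the first placebo dose. Section 9.7 gives "CFB = visit value – baseline value".

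Table 6 in Section 9.2 shows that placebo completers may enter the extension: "Subjects who complete the 52-week Double-blind placebo-controlled period will be offered participation in an optional open label, LTE period for an additional 2 years". They start evobrutinib 50 mg BID there. For the LTE, Section 9.7 says that the "start date of treatment is defined as the date of first treatment administration on or after the date of end of 52-week treatment".

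Table 26 in Section 15 selects "All data from LTE period (safety follow-up posterior to LTE included") for LTE safety and reports it by treatment sequence, with a Placebo/Evobrutinib 50 mg BID column. The safety sections then refer to baseline without redefining it:

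- **Laboratory, 15.3:** "A shift table of baseline versus post-baseline based on the worst NCI-CTCAE grade will be presented by treatment group for hematology and biochemistry".
- **Immunoglobulins, 15.8** (B cells in 15.9 are handled alike): "Descriptive statistics (absolute value, change from baseline and percent change from baseline) by treatment group and time point will be performed as well".
- **Vital signs, 15.4:** shift tables of maximum change, limited to systolic and diastolic pressure in the later analysis (abbreviated FA there, which I take to be the LTE analysis).
- **ECG, 15.5:** rhythm and morphology shifts from baseline into the LTE period.
- **UPCR, 15.12, and HBV DNA, 15.13:** shifts from baseline to extreme post-baseline values.

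Section 15.3 also starts the LTE time-to-event figures for ALT and eGFR at the 52-week baseline. LTE Day 1 serves as a second baseline only in Section 11.2.1, for SLE disease characteristics and CLASI.

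**The concern.** For the three groups randomized to evobrutinib, the 52-week baseline is the last value before active drug and is the natural safety reference. For switchers it is not: their last value before active drug is at LTE Day 1. One rule for all four columns means that the switcher column combines a year on placebo with the time on evobrutinib.

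This matters because Section 7 reduces the LTE analysis to a focus on safety. The switchers are the group in which the same subject is observed for a year without evobrutinib and then with it. A shift table that skips the value at the switch cannot show that contrast.

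**Working it through.** The SAP states no figure on this point, so there is none to reproduce. The check follows the baseline rule through the outputs.

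**Timing.** The windows in Section 18.11 count days as assessment date minus first dose date plus 1, and place Week 52 at Day 365. The baseline therefore lies 365 − 1 = 364 days before Week 52 at nominal timing. The first LTE dose falls on or after the end of 52-week treatment. A gap of 2 weeks, the threshold in Section 9.7, would make it 364 + 14 = 378 days.

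**Decomposition.** Let B0 be the 52-week baseline, B1 the LTE Day 1 value and X a value at an LTE visit. From the formula in Section 9.7:

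X − B0 = (X − B1) + (B1 − B0)

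For switchers, the first term arises on evobrutinib and the second before it. For the other three groups, both terms follow the start of evobrutinib.

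**By-visit summaries.** Section 18.11 defines an LTE Day 1 analysis visit for laboratory data (Table 53), liver tests (Table 55), immunoglobulins (Table 56), vital signs (Table 59) and B cells (Table 64). The LTE Day 1 row estimates the mean of B1 − B0, and a later row estimates the mean of X − B0. Their difference is the mean of X − B1 if the same subjects contribute to both rows. Recovery is only partial: the contributing subjects change over time, medians do not subtract, and percent changes remain scaled by B0.

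**Shift tables.** These cross-classify B0 with the post-baseline category, and B1 does not enter. Three hypothetical ALT grade histories for a switcher show the result:

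| History | B0 | B1 | Worst in LTE | Shift under 9.6 | Shift from LTE Day 1 |
|---|---|---|---|---|---|
| Rise on placebo, persists | 0 | 2 | 2 | 0 to 2 | 2 to 2 |
| Rise after the switch | 0 | 0 | 2 | 0 to 2 | 0 to 2 |
| Resolved on placebo, rises after the switch | 2 | 0 | 2 | 2 to 2 | 0 to 2 |

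Under Section 9.6 the first two histories fall in the same cell, although only the second is a change on evobrutinib. The third shows no shift although the grade rose on evobrutinib. The same reasoning applies to the blood-pressure maximum-change, ECG, UPCR and HBV DNA tables.

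**ALT and eGFR curves.** With the origin at the 52-week baseline, the first year of a switcher's curve is placebo time. The SAP does not say whether events in that year count. If they do, placebo events enter an LTE figure. If only LTE data are used, as in Table 26, no event can occur during that year. Neither reading gives time from the start of evobrutinib. The eGFR figure also admits only subjects with a baseline of at least 60 mL/min/1.73m², so for switchers its risk set is fixed a year before the switch.

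**The case against.** The case for the plan has weight:

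- **The choice is deliberate.** Section 3 lists a change in the LTE baseline definition for Version 4.0, and one reference keeps the four columns comparable. This stands, and it is why the 52-week version should be kept as supplementary.
- **Columns are labelled by sequence.** A reader might infer that the plan pools switchers with continuous evobrutinib subjects, or formally attributes their changes to the drug. Tables 6 and 26 do not support that, and the LTE laboratory output is descriptive.
- **By-visit output can be read against LTE Day 1.** A reader might infer that a real change after the switch is hidden there. Where an LTE Day 1 value exists, it largely is not. This does not help the shift tables.
- **Signals have other routes.** Section 15.3 says that clinically significant laboratory abnormalities were recorded as adverse events, and it lists Grade 3 or higher hematology and biochemistry values and Grade 2 or higher AST, ALT and bilirubin. These help for individual subjects but do not correct the summary tables.

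Three further inferences fail. The LTE adverse-event tables are not affected, because Section 15.1 counts from the first LTE dose. That anchor differs from the laboratory baseline in all four columns, so the difference is no argument about switchers in particular. Nor should one conclude that abnormalities resolved on placebo enter the LTE shift tables: the on-treatment definition starts at the first IMP dose, but Table 26 limits the data to the LTE period. Finally, the efficacy baseline in Section 14.6 is a separate, explicit choice and is not in question.

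**Conclusion.** The point holds for LTE safety output in the Placebo/Evobrutinib 50 mg BID column. The shift and maximum-change tables count abnormalities that arose on placebo and persisted, and they cannot be divided into placebo and evobrutinib periods. By-visit change summaries carry the same offset, B1 − B0, which a reader can partly remove. The ALT and eGFR curves include the placebo year on their time axis.

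The scope is one of four columns in descriptive tables of a terminated study, with no effect on the primary or key secondary conclusions. The SAP gives neither the number of switchers nor a rate of grade change on placebo, so I put no percentage on it. The conclusion assumes that Section 9.6 applies to safety as written, since no exception is stated, and that Table 26 governs which data enter.

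**What to change.** In Section 9.6, add that for LTE safety change-from-baseline and shift outputs the baseline of the Placebo/Evobrutinib 50 mg BID group is the last value on or before the first evobrutinib dose. Keep the 52-week baseline for the three evobrutinib groups and for all efficacy endpoints.

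In Section 15.3, start this group's LTE ALT and eGFR curves at the first evobrutinib dose, and apply the eGFR entry condition to the new baseline.

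Keep the 52-week-baseline version for switchers as a supplementary table, so that the four columns can still be compared on a common reference.

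The cost is one extra baseline flag, one supplementary set of tables and a footnote. LTE Day 1 visits are already defined for these data and Section 11.2.1 already uses LTE Day 1 as a second baseline, so no new data collection is needed. The downside is two baseline definitions in one table, which the footnote must explain.

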9.7 Other Specifications

Derivation of Age (years):

Age will be derived according to the following formula:

$$\text{Age (Years)} = \frac{(\text{date of given informed consent} - \text{date of birth} + 1)}{365.25}$$

In case of missing day for the date of birth, but month and year available, the day of birth will be set to 1 in the formula above. In case of missing day and month, they will both be set to 1.

Definition of Change from Baseline (CFB):

CFB and percent CFB will be computed as follows:

- CFB = visit value – baseline value
- Percent CFB = 100 * (visit value – baseline value) / baseline value

Definition of duration:

Unless otherwise specified, duration will be calculated as the difference between start and stop date + 1 (eg, duration of AE (days) = AE stop date – AE start date + 1). Unless otherwise specified, missing dates will not be imputed.

Conversion factors:

The following conversion factors will be used to convert days into months or years: 1 month = 30.4375 days, 1 year = 365.25 days. For time windows calculation, 1 month is expressed as 30 days.

Definition of Body Mass Index (BMI) (kg/m²):

BMI is defined as weight / (height²), where weight is expressed in kg and height in m. The BMI is available in the vs1 form of the Case Report Form, electronic (eCRF) and will not be re-derived.

Handling of missing data:

For efficacy analysis, methods of missing data handling are detailed in Section 14.

Unless otherwise specified, missing data will not be replaced.

In all subject data listings, imputed values will be presented and will be flagged. Non-imputed partial dates will be presented in a format such as “____YYYY”. Where imputation is defined, an imputed date with flag (i.e., D for day, M for month) will be reported.

Missing statistics, e.g., when they cannot be calculated, should be presented as ‘nd’ (denoting “Not Done”). For example, if n=1, the measure of variability (SD) cannot be computed and should be presented as ‘nd’. In case of zero records, an empty output with 0 occurrences, or a sentence mentioning that there are no data, will be presented. For tables of AEs and Deaths (outputs required for EudraCT and/or clinicaltrial.gov), if there are no observations, the output must contain the first line ‘Subjects with...’ or ‘Subjects who died’ displayed with 0 occurrence.

If the System Organ Class (SOC) or Anatomical Therapeutic Class (ATC) term is missing/not coded yet, then ‘Uncoded SOC’ (or ‘Uncoded ATC’) will be indicated at the TLF level. When a Preferred Term (PT) is missing, it will be set to ‘Uncoded PT: verbatim text’.

Treatment day:

Treatment day is defined as relative day to the start date of treatment. Treatment day will be calculated as the number of days since the first administration of any IMP. The day before is defined as Treatment day –1 (no Treatment day 0 is defined). Treatment day will only be presented in subject safety data listings.

For the 52-week treatment period, start date of treatment is defined as the date of first administration of randomized study drug.

For the LTE treatment period, start date of treatment is defined as the date of first treatment administration on or after the date of end of 52-week treatment.

On-Treatment flag:

On-treatment values are results of assessments done from the first IMP administration on Day 1 till End of Study (completion or early termination).

Repeated and unscheduled measurements:

Repeated and unscheduled measurements are included in the listings. Data collected at both unscheduled and scheduled visits will be used for shift tables. For summary statistics, figures, or inferential analysis, data are re-allocated to an analysis visit using time window calculations (see below).

Gap between 52-Week treatment period and LTE treatment period:

Subjects with a gap greater than or equal to 2 weeks between 52-Week treatment period and LTE period will be analyzed the same way as subjects without a gap. The gap will be defined using the last dose received during the 52-week treatment period and the first dose received during the LTE treatment period. Specific data listings on safety data (AEs and laboratory data) collected during the gap period will be produced for these subjects for the LTE analysis. In addition, for the subgroup of subjects with a gap greater than or equal to 2 weeks, the following analyses will be provided:

- Summary statistics of the gap duration
- SLE disease baseline characteristics at LTE Day 1
- SRI-4 response and SRI-6 response among HDA subjects by LTE visit

Time windows:

For efficacy and safety analyses, each measurement will be assigned an analysis visit number first according to the prespecified time window. The analysis visit will then be used for missing data imputations, analysis variable derivations, statistical calculations and presentations. Safety follow-up will not be included in analysis visit calculations, only assessments collected under treatment visits and no more than 14 days after last exposure date will be used.

For by visit summary of safety endpoints (e.g. laboratory and vital sign assessments), data collected during the safety follow-up will be shown, presenting separately data from subjects who completed safety follow-up and who discontinued during safety follow-up.

For subject data listings by time point, the nominal visit (as collected in the database) as well as the analysis visit will be displayed.

For the calculation of analysis visit using the time windows, 1 month is expressed as 30 days.

[figure not shown]
As the schedule of assessments is different for each visit, specific time windows must be used for each endpoint. They are defined in Appendix 18.11.

If there are multiple assessments within a same visit window, then the one closest to the target day will be used. If two assessments have the same difference with target day, the earlier one will be used.

Unblinding:

Details regarding the unblinding process are available in the Unblinding Plan.

CCI

10 Trial Subjects

The subsections in this section include specifications for reporting subject disposition and treatment/trial discontinuations. Additionally, procedures for reporting protocol deviations are provided.

